Basic investigations postulate that an imbalance between neurotransmitters regulating the stress and anti-stress systems underlie negative reinforcement and relapse in addiction. Nociceptin, which binds to the nociceptin/orphanin FQ peptide (NOP) receptor, is one such neuropeptide transmitter that exerts its anti-stress effects by counteracting the functional effects of corticotropin-releasing factor (CRF), the primary stress-mediating neuropeptide transmitter in the brain. Basic investigations suggest that CRF and nociceptin facilitate and inhibit anxiety-like behaviors, respectively. Convergent with this is data from animal models of alcoholism that support increased CRF and decreased nociceptin levels in the extended amygdala as the reason for anxiety-like behaviors that underlie relapse in addiction. This postulation is further supported by the ability of CRF1 receptor antagonists and NOP receptor agonists to blunt the reinforcing and motivational effects of alcohol on a range of addictive behaviors. Thus, it is of considerable interest to develop a methodology to examine CRF-NOP interactions in human addicts. Here, we will evaluate healthy humans with [C-11]NOP-1A and PET to determine if hydrocortisone-induced increases in amygdala CRF leads to altered NOP receptor binding. This experiment will for the first time document an in vivo interaction between CRF and NOP, and set the stage for evaluating if this interaction is abnormal in addiction in future investigations.

CS2.2

Select the category that best describes your research:

Biomedical research

[\[reviewer notes-\]](#)CS3.0 **Name of the Principal Investigator:**[[name]](#)

Note: Adjunct faculty of the University, including lecturers and instructors, are not permitted to serve as a PI or Faculty Mentor but may serve as co-investigators. Refer to [Chapter 4](#) on the HRPO website for more information.

CS3.1 **Affiliation of Principal Investigator:**

UPitt faculty member

If you chose any of the **Pitt options**, please indicate the specific campus:[Main Campus - Pittsburgh](#)If you chose the UPitt faculty member option, provide the PI's **University Faculty Title**:

Associate Professor

CS3.2

Address of Principal Investigator:[name]
[name]
Pittsburgh, PA 15213CS3.3 **Recorded Primary Affiliation of the Principal Investigator:**

U of Pgh | School of Medicine | Psychiatry

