
A3. Imaging of NOP receptors with [C-11]NOP-1A and PET

In a major advancement, the imaging group at NIMH recently radiolabeled and successfully validated a NOP receptor antagonist radiotracer [C-11] (S)-3-(2'-fluoro-6',7'-dihydrospiro[piperidine-4,4'-thieno[3,2-c]pyran]-1-yl)-2-(2-fluorobenzyl)-N-methylpropanamide (NOP-1A) for use in humans (Pike et al., 2011). [C-11]NOP-1A binds with relatively high affinity to NOP receptors (KD, 0.15 nM). [C-11]NOP-1A total uptake in various brain regions (VT) is consistent with the known distribution of NOP receptors in human and primate brain (relatively

high density in amygdala, striatum and cerebral cortex; and moderate density in cerebellum and midbrain) (Berthele et al., 2003; Bridge et al., 2003; Kimura et al., 2011; Lohith et al., 2012). Blocking studies in primates with the specific NOP receptor antagonist SB-612111 (KD 0.33 nM, 1mg/kg intravenously) indicate that 50-70% of [C-11]NOP-1A VT in brain regions represents specific binding to NOP receptors (Kimura et al., 2011). [C-11]NOP-1A demonstrates desirable pharmacokinetics in humans: brain uptake peaks relatively quickly (~ 10 min) and washes out rapidly; brain data is modeled well by a 2-tissue compartment kinetic analysis; VT values in brain regions range from 7 to 15; VT remains stable following 70 min of data acquisition; and the test-retest variability for VT is an acceptable $\leq 15\%$ in all brain regions (Lohith et al., 2014; Lohith et al., 2012).

[C-11]NOP-1A has been administered to approximately 50 subjects at the University of Pittsburgh PET facility by the PI in his prior research studies. Subject populations that it has been administered to include healthy subjects, alcoholics, cocaine addicts and PTSD subjects. To date no adverse reactions have been reported with its use.

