All tests for this research study will be performed at either the MR Research Center (MRRC) on the 8th floor of UPMC Presbyterian University Hospital (PUH) or the PET Facility on the 9th floor of UPMC PUH (directly above the MRRC).

The goal of the study is to determine if [C-11]NOP-1A receptor binding (VT) can be altered by an intravenous hydrocortisone (cortisol) challenge through CRF-NOP interactions. Twenty healthy control subjects will be studied twice with [C-11]NOP-1A before and after an intravenous hydrocortisone challenge (1 mg/Kg).

SPECIFIC METHODS AND DESIGN

1). MRI Protocol

Structural MRI: All female participants will undergo a urine pregnancy test prior to MRI. Subjects will undergo an MRI procedure for anatomical localization of regions-of-interest (ROI).

Participants with a questionable history of metallic fragments will not be included in the study. A single MRI study will be performed prior to the first PET study. The MRI examinations will be conducted on the 8th floor in the UPMC MRRC, which is located directly below the PET Facility, using a 3T scanner. A volumetric MPRAGE sequence will provide the anatomical framework for ROI analysis. This sequence is optimized to maximize the contrast among gray matter, white matter, and cerebral spinal fluid and provides high-resolution delineation of cortical and

subcortical structures. Imaging time for this pulse sequence is less than 8 minutes, with total time for the MRI scan estimated at 30 minutes. MRI data will be transferred to the PET Facility over the electronic network and co-registered with the PET data on a SUN Workstation using software routinely used for this purpose (Woods et al., 1992). The registered MRI will be used as an individualized anatomic map for the selection of ROIs used in the analysis of the PET data. The MRI might be obtained on the same day as a PET scan when possible to reduce transportation costs and inconvenience. Finally, the MRI will not be repeated if they have been performed under another IRB approved Psychiatric Molecular Imaging Program (PMIP) protocol within the past 6 months.

II). PET Protocol

PET scans will be acquired at the 9th floor PET Facility at UPMC PUH using a Siemens PET/CT (3D acquisition mode) scanner. Each participant will receive both a baseline [C-11]NOP-1A PET scan and post-hydrocortisone [C-11]NOP-1A PET scan following hydrocortisone administration in order to examine CRF-NOP receptor interactions.

Subject Preparation:

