
I). At the end of this scan, the subject will be provided a brief (~5 to 10 min) break to relax out of the scanner.

J). Subjects will then be administered 1 mg/kg of intravenous hydrocortisone as a bolus over 90 seconds. Following this, subjects will be monitored by the investigative team for subjective and objective adverse events (see monitoring listed below).

K). A second low-dose CT scan and [C-11]NOP-1A scan will be acquired a minimum of 3.5-hours post hydrocortisone, identical to the methods outlined previously. The timing of the second [C-11]NOP-1A administration and subsequent PET scanning (i.e., ~ 3.5 to 4.5 hours) is based on previous basic science studies that have documented CRF-NOP interactions (Ciccocioppo et al., 2014a; Rodi et al., 2008). The proposed timing will also ensure that the maximum increase in amygdala cortisol and CRF ($T_{max} \sim 25$ to 30 min) following intravenous hydrocortisone (1mg/kg) has occurred prior to the PET scan (Cook, 2002).

Blood Sampling during [C-11]NOP-1A PET scans: Periodic arterial blood sampling will be performed during the PET studies for the quantitative data analyses (i.e. measurement of the radiotracer and its metabolites in the blood). These blood draws will not exceed 130 ml (about 9 tablespoonfuls) of blood in total. For each PET scans, hand-drawn arterial blood samples (0.5 ml) will be collected throughout the scan with no more than 20 collected during the first 2 min and no more than 15 collected at intervals of increasing duration minutes (no more than 35 total samples). Also, larger blood samples (3-5 ml) will be obtained at no more than 8 times during each PET scan for the determination of radiolabeled metabolites and protein binding. This would amount to no more than 43 arterial samples and a blood volume loss of no more than 60 ml (4-5 tablespoonfuls)/scan ($60 * 2 \text{ scans} = 120 \text{ mL}$). In addition to this two 3-5 mL blood samples will be drawn for measuring cortisol plasma levels for each post-hydrocortisone scan ($2 * 5 * 1 \text{ scan} = 10 \text{ mL}$). The timing of these cortisol blood samples will be $t=0$ and 1h post-hydrocortisone

L). Following this scan, all subjects will receive:

1. Physical Exam.
2. Mental Status Exam.
3. EKG.
4. Vital Signs measurement.

M). The subject will be evaluated by a physician to ensure they meet the following discharge criteria:

1. a blood pressure of $> 90/60$ and $< 150/90$.
2. a heart rate > 50 or < 110 .

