and drug use disorders. The only information documented is the relationship to the participant and that no names, date of birth or other identifiers will be documented.

2.16.2

If the information about the third party is of a private nature, can the identity of the third party be readily ascertained or associated with this information?

*

No

Describe the **private information** that will be collected and recorded about the third party: We simply intend to ask information from subjects---medical illness, mental illness and drug and alcohol use in first- and second-degree relatives---to determine items which would be exclusionary for the subject's participation in this study, or related to imaging outcome measures derived in the subject. This information will be no different than the family history obtained during a routine physical and psychiatric exam.

[\[reviewer notes-\]](#)

2.17 What are the main outcome variables that will be evaluated in this study?

The main outcome measure will be the change in [C-11]NOP-1A VT elicited by hydrocortisone-stimulated CRF (Δ VT). Δ VT will be calculated as the difference between VT measured in the post-hydrocortisone condition and VT measured in the baseline condition on that day (VT BASE), and expressed as a percentage of VT BASE.

2.18 Describe the statistical approaches that will be used to analyze the study data.

* Addressed below:

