To determine if [C-11]NOP-1A receptor binding (VT) is increased following the administration of hydrocortisone. This would suggest that there is a compensatory upregulation of NOP receptors to enhance transmission at this site in response to CRF release. Such an interpretation would be consistent with nociceptin, a component of the brain's anti-stress system counteracting CRF, a component of the brain's stress system. The change in [C-11]NOP-1A VT elicited by hydrocortisone-stimulated CRF (Δ VT) will be calculated as the difference between VT measured in the post-hydrocortisone condition and VT measured in the baseline condition on that day (VT BASE), and expressed as a percentage of VT BASE. Scan parameters between baseline and post-hydrocortisone conditions will be performed with paired t-tests. The effect of hydrocortisone on [C-11]NOP-1A VT will be evaluated in the individual ROIs with two tailed paired t-tests. A false discovery rate (FDR) correction with $\alpha = 0.05$ will be applied to correct for multiple comparisons in the ROIs (Benjamini and Hochberg, 1995). Exploratory analyses will be performed using a LMM to evaluate the effects of gender on change in [C-11]NOP-1A VT (Δ VT) elicited by hydrocortisone-stimulated CRF. The effect of hydrocortisone on [C-11]NOP-1A VT in high (e.g., amygdala) and low binding regions (e.g., midbrain, cerebellum) will be contrasted as well. Hydrocortisone-induced changes in clinical variables such as PSS, HAM-A, Heart rate variability, and skin conductance (from E4 wrist band) will also be correlated with the Δ [C-11]NOP-1A VT.

[\[reviewer notes-\]](#)

2.19

Will this research be conducted in (a) a foreign country and/or (b) at a site (e.g., Navajo Nation) where the cultural background of the subject population differs substantially from that of Pittsburgh and its surrounding communities?

* No

Note that copies of training records, licenses, certificates should be maintained in the study regulatory binder and are subject to audit by the Research Conduct and Compliance Office (RCCO).

In addition, individuals planning to conduct human subject research outside the United States must complete an optional module on the CITI training website: International Studies. [Click here](#) to access the instruction sheet for accessing optional CITI modules.

[\[reviewer notes-\]](#)

2.21

Will this research study be conducted within a nursing home located in Pennsylvania?

* No

[\[reviewer notes-\]](#)

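### The uncontrolled before/after design can show a change in VT after hydrocortisone but cannot attribute it to CRF, as 2.17 and the abstract do, and 2.18 states no use of the protein-binding data

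*Combined protocol and SAP*

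**What the plan says.** Sections 2.3 and 2.3.1 describe an experimental, open-label study without a placebo arm. In 2.6 all subjects "will be studied twice with [C-11]NOP-1A before and after an intravenous hydrocortisone challenge": a baseline scan, a short break, the challenge, and a second scan at least 3.5 hours later. No subject has a repeat scan without the drug. The challenge is assayed only by plasma cortisol at 0 and 1 hour; CRF is not measured.

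Section 2.17 states: "The main outcome measure will be the change in [C-11]NOP-1A VT elicited by hydrocortisone-stimulated CRF". It then defines the quantity neutrally, as post-hydrocortisone VT minus baseline VT, as a percentage of baseline. Section 2.18 repeats the label ("The change in [C-11]NOP-1A VT elicited by hydrocortisone-stimulated CRF"). The abstract goes further: "This experiment will for the first time document an in vivo interaction between CRF and NOP". Aim 1 in 1.2 and the opening of 2.18 are conditional, saying what a rise would suggest.

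Section 2.6 also says that the tracer has no reference region, so an arterial input is needed. Larger blood samples are drawn in each scan "for the determination of radiolabeled metabolites and protein binding". Section 2.18 does not mention protein binding or free fraction. It says "Scan parameters between baseline and post-hydrocortisone conditions will be performed with paired t-tests" without listing the parameters. The main analysis is a two-tailed paired t-test in each ROI with FDR control. A regional comparison is also planned: "The effect of hydrocortisone on [C-11]NOP-1A VT in high (e.g., amygdala) and low binding regions (e.g., midbrain, cerebellum) will be contrasted as well". Its scale is not given.

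**The concern.** A paired t-test on scan 2 minus scan 1 tests whether the mean change is zero. Without a control pair, anything that differs systematically between the scans enters that mean: the drug acting through CRF, the drug acting otherwise, time of day, and session effects. The cited test-retest work is used only for variability (1.3 and 3.12); the documents report no mean test-retest change from it.

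Free fraction is the alternative that the study could examine with samples it already takes. In the standard model (an assumption here), VT is proportional to plasma free fraction, so a relative change in free fraction produces the same relative change in VT in every ROI. FDR control gives no protection. The null hypothesis in each ROI is that VT did not change, and under such a shift that null is false everywhere. The rejections would be correct about VT and wrong only as statements about receptors.

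The consequences reach beyond this study. Section 3.12 says that it will supply the effect size for a later, adequately powered investigation, and 1.2 and 1.3 say that success would support using the paradigm in addiction.

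**Working it through.** **Inputs.** From 3.12: n = 16, an assumed 10% rise in VT, within-subject variability of 10% to 14%, two-tailed paired t-test at 0.05, stated power 0.96 to 0.76. The shift sizes, free-fraction SDs and correlations below are assumptions; the documents give none of them.

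**Step 1: reproduce the stated power.** Take 10% and 14% as the SD of the percentage change. The noncentrality is (effect/SD) × √n with 15 degrees of freedom.

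- SD 10%: (10/10) × 4 = 4.00, power 0.962.
- SD 14%: (10/14) × 4 = 2.86, power 0.761.

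Both match 3.12, so the same test can be used below.

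**Step 2: put in a shift common to all ROIs, with no receptor effect.** Probability that one ROI reaches p < 0.05 before FDR, n = 16:

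| Assumed shift | Noncentrality (SD 10% / 14%) | P, SD 10% | P, SD 14% |
|---|---|---|---|
| 2.5% | 1.00 / 0.71 | 0.155 | 0.103 |
| 5% | 2.00 / 1.43 | 0.465 | 0.267 |
| 7.5% | 3.00 / 2.14 | 0.801 | 0.518 |
| 10% | 4.00 / 2.86 | 0.962 | 0.761 |

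The last row equals the planned power, because the test cannot tell a 10% common shift from a 10% CRF effect. More subjects do not help: at n = 20 a 5% shift gives 0.565 / 0.329. FDR lowers the figures for a given ROI without removing the problem. In a simulation of the 5% shift with 5 or 10 ROIs and inter-ROI correlations of 0.5 to 0.9 (assumed), the amygdala is rejected in 0.316–0.375 of studies at SD 10% and 0.137–0.191 at SD 14%.

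**Step 3: is a test of free fraction alone enough?** A 5% shift in free fraction is detected at n = 16 with probability 0.962 if the SD of its change is 5%, but 0.465 if it is 10%. A non-significant comparison may therefore not be reassuring, which is why the estimate on VT divided by free fraction is needed as well.

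**Step 4: what the corrected analysis costs in precision.** For small changes, the SD of the percentage change in VT divided by free fraction is √(SD_VT² + SD_f² − 2r·SD_VT·SD_f). Power for a 10% effect, n = 16:

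| SD_VT | SD_f | r = 0: SD, power | r = 0.5: SD, power |
|---|---|---|---|
| 10% | 5% | 11.2, 0.92 | 8.7, 0.99 |
| 10% | 10% | 14.1, 0.75 | 10.0, 0.96 |
| 14% | 5% | 14.9, 0.71 | 12.3, 0.86 |
| 14% | 10% | 17.2, 0.59 | 12.5, 0.85 |

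The analysis is noisier if the two vary independently. At r = 0.5 it loses nothing. Proportionality of VT to free fraction would itself induce a positive correlation, but measurement error in free fraction would weaken it.

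**Step 5: the regional contrast.** A common percentage shift cancels in a contrast of percentage changes. It does not cancel on absolute VT: section 1.3 (A3) says "VT values in brain regions range from 7 to 15", and a 5% shift at those ends is 15 × 0.05 = 0.75 units against 7 × 0.05 = 0.35, a difference of 0.40. The scale therefore matters if the contrast is read as evidence of regional specificity.

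**The case against.** The strongest reply is that the plan is more careful than its labels. Aim 1 and 2.18 say only what a positive result would suggest, 1.3 (A4) says what it would support, and 3.12 presents the study as groundwork for a powered investigation. After the CRF label, 2.17 gives a neutral formula, so rewording changes no number. All of this stands. A reader might infer that every significant increase will be reported as a proven CRF effect; the hedged passages do not support that. What remains is an outcome definition and an abstract sentence that say more than the design and the rest of the plan allow.

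Second, nothing in the documents suggests that hydrocortisone alters the tracer's protein binding 3.5 hours later. That is also correct. A reader might take the table as an estimate of the false-positive risk; it shows sensitivity to an assumed shift, and at 2.5% the excess over 5% is modest.

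Third, free fraction may already be meant among the scan parameters, since protein binding is sampled for the quantitative analysis. It may be, but the list is not given, and step 3 shows why a significance test alone may not settle the matter.

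Fourth, the contrast has a natural percentage reading, because the only change measure defined is a percentage. A reader might infer that the plan's artefact check stands or falls on an unstated scale, but the documents never give the contrast that role. Even on percentages it cannot separate a plasma shift from a brain-wide receptor rise, because midbrain and cerebellum also contain NOP receptors. The scale is a minor clarification.

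**Conclusion.** The point holds as a limit on attribution and a gap in the analysis plan. A significant paired test would establish a change in VT after hydrocortisone; the design cannot assign it to CRF, and the outcome definition and abstract should not do so. The sample-size calculation is not in error: its power figures reproduce.

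The size of the free-fraction problem is unknown. Over assumed common shifts of 2.5% to 10%, the chance that a single ROI is significant with no receptor effect runs from 16% to 96% at SD 10% and from 10% to 76% at SD 14%. These figures rest on proportionality of VT to free fraction, on 3.12's variability being the SD of the percentage change, and on n = 16; they are before FDR. The change is worth making because the samples are already planned and the primary test need not move. Confidence is medium.

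**What to change.** (a) In 2.18, name plasma free fraction among the parameters compared between conditions. Prespecify a sensitivity analysis that repeats the paired analysis on VT divided by free fraction. Report both estimates with 95% confidence intervals, and leave the primary test on VT unchanged.

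(b) In 2.17, and where 2.18 repeats it, define the outcome as the percentage change in VT after hydrocortisone. In the abstract, replace the claim to document an interaction with wording such as *findings consistent with* one.

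As a minor clarification, state that the high- versus low-binding contrast is run on percentage change in VT, and that a null contrast does not exclude a diffuse receptor effect.

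The cost is one extra analysis of data already collected, a few sentences and a more modest claim; no scans, samples or subjects are added. The corrected analysis may be less precise (step 4), which is why it should be a sensitivity analysis only. Time-of-day and session effects are not removed by any of this; only the wording in (b) deals with them.

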Medical test results will be reviewed prior to study entry. The laboratory tests will not be repeated if they have been performed within the past six months. [Note that the serum pregnancy test, and urine toxicology prior to PET scans will not fall into this category]. In addition, other study measures such as MRIs and cognitive tasks will not be repeated if they have been performed under another IRB approved Psychiatric Molecular Imaging Program (PMIP) protocol within the past 6 months.

(4) Stress and anxiety rating scales:

(a) Perceived stress scale (PSS) (Cohen et al., 1983): A 14-item scale that measures the degree to which situations in an individual's life are appraised as stressful.

(b) Hamilton Anxiety Rating Scale (HAM A) (Hamilton, 1959): A 14-item scale that measures anxiety-like symptoms.

(c) Center for Epidemiological Studies in Depression (CES-D): A 20 item scale that measures depression.

The records of the subjects who fail screening after signing consent are not destroyed, but maintained as any subject who continues the research study with the reason for exclusion mentioned in it.

All clinical assessments, including the SCID will be administered by research coordinators and co-investigators as delegated by the PI. The PI will supervise the research coordinators till they are deemed competent to do it on their own; He will also assist them as questions arise in the future.

Screening procedures may be done after initiation or completion of the experimental procedures

depending on MRI and PET schedules because this is a study that involves healthy controls. For example, rating scales such as HAM-A, PSS, CES-D, etc., that do not determine a subject's inclusions/exclusion may be done on the day, or even after scans. It may also involve doing a MRI before labs, if the subject has no contraindications on the PET/MRI screening. However, a PET will not be done before completion of the SCID and labs because they are necessary to rule out low hemoglobin, current psych and drug use disorders etc.)

[\[reviewer notes-\]](#)

2.6

Provide a detailed description of all research activities (e.g., all drugs or devices; psychosocial interventions or measures) that will be performed for the purpose of this research study.

This description of activities should be complete and of sufficient detail to permit an assessment of associated risks.

At a minimum the description should include:

- **all research activities**

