3. no reported subjective or objective side effects from the hydrocortisone at discharge.
4. a normal EKG (or not clinically significant, or no change from baseline EKG as determined by a physician)
5. a normal physical exam.
6. a normal mental status exam.

N). Healthy control who meet the above listed criteria following the PET scans will be

discharged home.

SUBJECT MONITORING:

A). Subject monitoring prior to the PET Scan

1. A physician will review screening labs, EKG and medical evaluation (see attached) prior to scan day.
2. Baseline review of systems and medication history (to document no change from screening).
3. Vital signs.
4. Urine toxicology screen.
5. A statement of use of a method of contraception for all subjects in the past 15 days (abstinence, barrier methods, oral contraceptive medications, etc.).
6. All female subjects of child bearing potential will undergo urine pregnancy testing to rule out pregnancy on the day of the PET scans prior to any of the PET scanning procedures.

B). Subject monitoring during PET scans

1. An experienced technician will be in both visual and verbal contact with the participant at all times during the study. If the participant voices any difficulty or desires to be removed from the scanner, or if the technician sees any indication that the participant is experiencing discomfort, the participant will be immediately removed from the scanner and verbally reassured.

C). Subject monitoring on hydrocortisone

1. The hydrocortisone will be administered by a physician investigator familiar with the protocol. The physician investigator will also be available in the PET facility to monitor the subject on hydrocortisone.
2. Blood pressure and heart rate will be recorded once prior to hydrocortisone and following hydrocortisone every ten minutes for the first 60 minutes, then every 15 minutes thereafter (up to at least 120 min).
3. Subjects will be assessed once at baseline (time 0), once at 60 minutes post-hydrocortisone (t=60 min), and once before the second [C-11]NOP scan with visual analog scales such as the PSS, HAM-A and CES D (scales attached in 2.8) to evaluate their subjective feelings while on hydrocortisone.

2.6.1

Will blood samples be obtained as part of this research study?

* Yes

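### Section 2.6 calls PSS, HAM-A and CES-D visual analog scales and repeats them within hours; PSS change, at least, is a poor input to the planned correlation with ΔVT

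*Combined protocol and SAP*

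**What the plan says.** Section 2.6, under subject monitoring on hydrocortisone, sets the schedule: "Subjects will be assessed once at baseline (time 0), once at 60 minutes post-hydrocortisone (t=60 min), and once before the second" scan. The second scan starts no earlier than 3.5 hours after the bolus. The assessment is to be made "with visual analog scales such as the PSS, HAM-A and CES D", and its stated purpose is "to evaluate their subjective feelings while on hydrocortisone".

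Section 2.5.1, item (4), describes the same instruments under screening:

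- PSS: "A 14-item scale that measures the degree to which situations in an individual's life are appraised as stressful"
- HAM-A: "A 14-item scale that measures anxiety-like symptoms"
- CES-D: "A 20 item scale that measures depression"

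Section 2.8 asks for every instrument except the SCID and KSADS to be uploaded, and lists three files: PSS, CES-D and HAM-A.

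Section 2.18 then plans to correlate "Hydrocortisone-induced changes in clinical variables such as PSS, HAM-A, Heart rate variability, and skin conductance" with ΔVT. CES-D is not named there. The section does not say which post-dose assessment, 60 minutes or pre-scan, defines the change.

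**The concern.** Two things do not fit together. The label in 2.6 contradicts the description in 2.5.1. And the purpose in 2.6, an acute response to a bolus, does not match what 2.5.1 says the PSS measures. Appraisal of one's life situations has little reason to shift between the bolus and the next assessment an hour or a few hours later.

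What is at stake is how the correlation in 2.18 can be read. If PSS change shows no association with ΔVT, the reader cannot tell whether subjective stress is unrelated to the change in NOP binding or whether the instrument was unable to move in the time allowed. Momentary ratings that are not collected on the scan day cannot be recovered later.

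**Working it through.** **Is there a stated figure to reproduce?** Not for the scales: the plan gives no SD, reliability, recall period, expected change or power for them. Its only power statement (section 3.12) concerns VT. With n = 16, a 10% change, a two-sided 0.05 paired t-test and 15 degrees of freedom, the noncentrality is (10/SD)·√16. This is 4.00 at SD 10% and 2.86 at SD 14%, giving power 0.962 and 0.761. These match the stated 0.96 and 0.76 but have no bearing on the scales.

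**The sections side by side**

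| Instrument | 2.6 label | 2.5.1 description | Named in 2.18 | Does the visible text bear on change within 1 to 4 hours? |
|---|---|---|---|---|
| PSS | visual analog | 14 items, appraisal of life situations | yes | Yes, against it |
| HAM-A | visual analog | 14 items, anxiety-like symptoms | yes | No |
| CES-D | visual analog | 20 items, depression | no | No |

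The label is contradicted for all three. The doubt about responsiveness has textual support only for the PSS.

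**Can the loss be sized?** Take equal variances on the two occasions and independent errors. The reliability of a change score is then (r_xx − r_12)/(1 − r_12), where r_xx is single-occasion reliability and r_12 the correlation between occasions. All inputs are assumptions:

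- r_xx 0.7, r_12 0.5: 0.2/0.5 = 0.40
- r_xx 0.8, r_12 0.5: 0.3/0.5 = 0.60
- r_xx 0.9, r_12 0.5: 0.4/0.5 = 0.80
- r_xx 0.8, r_12 0.7: 0.1/0.3 = 0.33
- r_xx 0.9, r_12 0.85: 0.05/0.15 = 0.33

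The range falls on both sides of 0.5, and the documents give nothing to choose within it.

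**What that range means for the correlation.** The critical |r| at two-sided 0.05 is t/√(n − 2 + t²), which is 0.497 at n = 16 and 0.444 at n = 20. Power by Fisher's z is Φ(atanh(r)·√(n − 3) − 1.96). With error-free measurement, 80% power needs r = 0.65 at n = 16 or 0.59 at n = 20. Unreliable change multiplies the true r by the square root of the change-score reliability. For a true r of 0.65 at n = 16:

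| Assumed change-score reliability | Expected observed r | Power |
|---|---|---|
| 0.8 | 0.58 | 67% |
| 0.6 | 0.50 | 52% |
| 0.5 | 0.46 | 43% |
| 0.3 | 0.36 | 27% |

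Power falls throughout, but whether the expected r stays above the critical value depends on the assumption: at 0.6 it is 0.65 × √0.6 = 0.503, just above 0.497. Small n is a separate limit that no instrument removes. A true r of 0.5 measured without error has only about 51% power at n = 16 and 62% at n = 20.

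**The case against.** The strongest reply is that the inconsistency may be one of wording only. The list in 2.6 is open-ended, the uploaded forms are not reproduced, and they may have been reworded for momentary use. Anxiety symptoms can plausibly change within hours, so HAM-A may serve its purpose. The scale correlations come last in 2.18, and the same sentence uses heart rate variability and skin conductance, recorded continuously by the wrist band. The acute response therefore does not rest on the scales alone.

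Most of this stands. It limits the point to what the visible text shows: three instruments under a label that does not fit them, no identified visual analog form, and one instrument whose description runs against its use. It does not remove the point. Section 2.8 calls for all instruments and lists only these three, and 2.18 names PSS change explicitly.

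Three stronger readings are tempting, and the documents support none of them.

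- A reader might infer that multi-item scales give change scores that are mostly noise. Having many items does not do that; item count does not enter the change-score formula, and more items usually raise single-occasion reliability.
- A reader might infer that the correlation is bound to be null. That would require all the scales to be incapable of moving, which the text does not show for HAM-A. It is also a different failure from noise: a scale that cannot move gives changes near zero.
- A reader might infer that monitoring of mood after hydrocortisone is deficient. Sections 2.6, 2.7 and 5.1.1 also provide observation for subjective and objective adverse events, a physician in the facility, a mental status exam, discharge criteria and a follow-up call.

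**Conclusion.** The mislabelling is certain from the text. It is also well supported, on the plan's own description, that PSS change over about 1 to 4 hours is a poor measure of acute response and a weak input to the correlation with ΔVT. For HAM-A the question is open, because neither a recall period nor evidence of short-term responsiveness is given. For CES-D it is open too, and has no named role in 2.18.

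No single figure for the loss is defensible. The conclusion for the PSS assumes that the uploaded form follows the 2.5.1 description and was not reworded for momentary use. The consequence is limited to an exploratory correlation. The main outcome in 2.17, percent change in VT, its power and the wrist-band measures are unaffected. This is a low-cost improvement and no threat to the study's main conclusion.

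**What to change.** 1. In 2.6, correct the label so that it agrees with 2.5.1.
2. Add a short form of true visual analog items, rated 0-100 for how the subject feels at that moment, covering anxiety, stress and mood. Give it at the three times already planned. This is what the wording of 2.6 already implies.
3. In 2.18, name the change in these items in place of PSS change, and state which post-dose time point defines it.
4. Keep PSS, HAM-A and CES-D as baseline descriptors, completed before the bolus. Section 2.5.1 currently allows them on the scan day or afterwards.

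The cost is one short extra form and a minor IRB modification. If the three scales are no longer repeated, repeated scores on established instruments are lost; keeping HAM-A at the later times would avoid that for one scale at the price of more subject time. The new items will not overcome the small sample, so the correlations should still be reported as exploratory.
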